TEG is limited, however, by the requirement that the analysis be performed within minutes of blood draw to prevent clot formation unless the addition of citrate occurs.³⁷ It has been demonstrated the TEG can assess coagulopathy, platelet dysfunction and most importantly, hyperfibrinolysis at an early stage following injury and is the most rapid available test for providing reliable information on coagulopathy in significantly injured patients.^{38,39} If not more important, the technology has been deemed feasible for use in a deployed military setting as well as for civilian use.⁴⁰

C.5. Early tranexamic acid reduces mortality post-injury:

In a large, civilian, multicenter, randomized, controlled trial (CRASH-2 trial) on the use of tranexamic acid in patients at risk of bleeding, a significant reduction in mortality was found with its use.⁴¹ Tranexamic acid is a lysine analog that is known to interfere with binding sites on plasminogen and inhibit fibrinolysis.⁴² Inclusion criteria for the trial included hypotension SBP <90 mm Hg or tachycardia (> 110 beats per min), in patients at risk of significant hemorrhage within 8 hours from injury. Dosing of tranexamic acid was given in a bolus 1 gram dose over approximately 10 minutes followed by an infusion dose (additional 1 gram) over eight hours. This therapy was subsequently found in exploratory analysis to be beneficial in those who received tranexamic acid in the first 3 hours from injury and strongest in those patients who received it in the first hour following injury.⁴³ Pre-specified analysis of the trial data demonstrated that the mortality benefit attributable to tranexamic

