C.7. Plasmin and its pro-inflammatory effects: Tranexamic acid is a lysine analogue that interferes with binding of plasminogen to fibrin, which is required for plasmin activation.⁴² Plasmin has pro-inflammatory effects by activating monocytes, neutrophils, platelets, endothelial and dendritic cells and induces pro-inflammatory genes.^{51,52} Plasmin also induces chemotaxis of monocytes and dendritic cells and in-vitro and in-vivo studies have demonstrated the ability of plasmin to stimulate the production reactive oxygen species and promote the release of lipid mediators and cytokines via complement activation.^{51,53} Tranexamic acid benefits in cardiac surgery have been hypothesized to be secondary to a reduction in the inflammatory response, possibly via a reduction of plasmin activation.⁵³⁻⁵⁵ The mortality benefit associated with tranexamic acid may occur secondary to an anti-inflammatory effect due to a reduction in plasmin activation. (Fig 4.)

C.8. Safety and dosing of tranexamic acid: Tranexamic acid has been most commonly used in cardiac surgery and orthopedic surgery for its blood transfusion reduction effects with the risks of thrombotic complications and post-operative seizures being the most common complications reported with its use.^{49,50,56,57} It has been retrospectively compared to other anti-fibrinolytics used in cardiac surgery and shown to have a similar or better safety profile in most studies. Post-operative seizures, due to a GABA receptor antagonist effect, have also been documented following cardiac surgery and this complication is thought to be a dose dependent effect.^{58,59} An orthopedic meta-analysis demonstrated no higher risk of venous thromboembolism following hip and knee replacement, surgeries typically thought to be at increased risk of thromboembolism.⁴⁹ The literature does suggest that further higher level studies are

[figure not shown]

Fig 4. Pro-inflammatory and coagulation system effects of plasmin. Levy JH. *Lancet*. 2010 Jul 3;376(9734):3-4

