levels, markers of complement activation, HMGB1 levels and the early inflammatory cytokine response as compared to standard dosing or abbreviated dosing.

F. Project Milestones:

The proposal is for a 3 year trial. The FDA approval process will be initiated after notification of proposal funding. Community notification and other procedures associated with exception from consent for emergency research will be initiated and completed prior to IRB approval at all institutions. Following final IRB approval a 1.5 month startup period will be utilized to verify and educate all centers prior to beginning enrollment. A data entry web based platform will be created during this same time period. Enrollment will occur for 33 months (2.75 years) with prospective data entry of laboratory and TEG measurements, clinical outcomes, transfusion requirements and demographic and injury characteristics. Serum for cytokine and ELISA measurements will be batched and sent to the University of Pittsburgh on an annual basis. We expect approximately 70 patients per year per institution on average. Flow cytometry for platelet and leukocyte activation and RT-PCR may be performed at the University of Pittsburgh prospectively on a subset of patient samples. Enrollment will be monitored on a semi-annual basis for each participating center. Data safety and monitoring over the course of the clinical trial will fall under the responsibility of an independent data safety and monitoring board (DSMB). Interim analysis will occur at 33% and 66% of patient enrollment. A 1.5 month data cleaning and wind down will occur once enrollment has been completed, allowing data analysis and manuscript preparation.

G. Military Significance/Public Purpose:

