H.3.1. Prehospital Phase Intervention: Once inclusion and exclusion are verified while the patient is being transported via emergency medical transport to a STAAMP trial participating center, in a randomized, double blinded fashion, either 1 gram bolus of tranexamic acid diluted in 100cc of normal saline (pre-prepared on emergency vehicle) or placebo of identical volume will be infused intravenously or intraosseously (if IO access was obtained due to a clinical need per standard of care) into the patient over approximately 10 minutes (“Bag A”). After receiving the prehospital phase intervention, standard operating procedures utilizing goal directed crystalloid infusion will be followed (see **H.7. Prehospital Standard Operating Procedures** below)

H.3.2. In-hospital Phase Intervention: Upon arrival, patient blood and labs will be sampled and arrival rapid-TEG analysis will be performed within first 6 hours. After inclusion and exclusion criteria verification by research staff, in a double blinded, randomized fashion, those patients who received tranexamic acid in the prehospital phase will receive 1 of 3 different dosage regimens:

1. Standard Tranexamic acid Dosing: 1 gram infusion over approximately 8 hours
2. Repeat Tranexamic acid Dosing: 1 gram bolus **and** 1 gram infusion over approximately 8 hours
3. Abbreviated Tranexamic acid Dosing: No further tranexamic acid to be given

For intervention blinding purposes, each patient will receive both a bolus dose (either tranexamic acid or placebo), “Bag B,” and 8 hour infusion (either tranexamic acid or placebo), “Bag C,” depending on the randomized dosing regimen. (Figure 13. below)

H.3.2.1 Adjustment For Renal Insufficiency: Subjects with a known or suspected history of renal insufficiency will receive a renal dose adjustment for the 8 hour repeat infusion (Bag C). The Estimated Body Weight Table will be used to determine the dose (Figure 12). The dose will be capped at 1000 mg.

1. Standard Dosing: bolus- no dose adjustment / infusion- 1.25 mg/kg/hr x 8hrs
2. Repeat Dosing: bolus- no dose adjustment / infusion- 1.25 mg/kg/hr x 8hrs
3. Abbreviated Dosing: bolus- no dose adjustment / infusion- 1.25 mg/kg/hr x 8hrs

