I.5. Laboratory/Mechanistic Outcome Methods/Definitions: All measurements will be performed within 6 hours of arrival and at 12 and 24 hours post injury (+/- 12 hours) for the randomized dosage regimen comparison. One more additional blood sample will be collected at 72 hours (\pm 12 hrs) for D-dimer, activated Protein C levels and plasmin-antiplasmin complexes measurements. Excluding r-TEG analysis and PT/ INR measurements, all blood and serum samples will be spun, stored and batched at their respective institution and delivered to the University of Pittsburgh where formal ELISA immunoassay measurements will be undertaken. Those laboratory/mechanistic outcomes including flow cytometry which require fresh blood samples will be performed only at the University of Pittsburgh on a subset of patient samples unless participating centers have specific capabilities and following appropriate training for standardization.

I.5.1. Coagulopathy and TEG parameters (Aim#2): To appropriately characterize differences in coagulopathy between tranexamic acid and placebo, in addition to r-TEG measurements of hyperfibrinolysis, presenting PT/ INR and additional TEG parameters will also be measured (ACT, r-value, k-time, α -angle, maximal amplitude, and G-values). All rapid TEG measurements will be performed within 6 hours of arrival and at 12 and 24 (+/- 12 hours) hours post injury. TEG analysis will be performed on a TEG[®] 5000 Thromboelastograph[®] Hemostasis Analyzer which will reside within the emergency department of each participating site. Standard laboratory INR will be drawn and measured at each institution within 6 hours of arrival and at 12 and 24 hours (+/- 12 hours). To further quantify the coagulopathy and hyperfibrinolysis post injury in these patients, D-dimer, activated Protein C levels and plasmin-antiplasmin complexes will be measured by ELISA plate assay. (ANIARA, USCN Life Science Inc., DRG International, Inc.) Plasmin-antiplasmin complexes may represent a more common, subclinical measurement of fibrinolytic activity that is not able to be assessed using standard TEG analysis, but elevated levels are associated with significantly worse outcome post injury and may be a marker than demonstrates the mechanism by which tranexamic acids has it beneficial effects.

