I.5.2. Exploratory Inflammatory Response Outcomes (Aim#3): Plasmin has pro-inflammatory effects by activating monocytes, neutrophils, platelets, endothelial and dendritic cells and induces pro-inflammatory genes.^{51,52} Plasmin also induces chemotaxis of monocytes and dendritic cells and in-vitro and in-vivo studies have demonstrated the ability of plasmin to stimulate the production reactive oxygen species and promote the release of lipid mediators and cytokines via complement activation.^{51,53} To appropriately characterize the potential non-antifibrinolytic mechanisms responsible for the mortality benefit attributable to tranexamic acid, serum plasmin levels, and plasmin mediated compliment activation (C3a and Factor B) and HMGB1 levels will be measured by ELISA plate assay for all enrolled patients (MyBioSource, BD Biosciences). A Cytokine 10-plex Panel for the Luminex[®] platform will be utilized for all early inflammatory cytokine measurements. (Novex[®]) These same inflammatory response measurements will be utilized for the randomized dose regimen comparison at 12 and 24 hours post injury.

I.5.3. Platelet, Leukocyte and Inflammatory Gene Expression Measurements (Aim#3): To further characterize an anti-inflammatory effect of tranexamic acid mediated thru reduced plasmin activation, for those patients enrolled at the University of Pittsburgh, whole fresh blood will be obtained and platelet and leukocyte activation will be measured on a subset of patient samples using flow cytometry (FACS) analysis utilizing platelet activation specific antibodies (CD41 and CD62P, Molecular Probes[®]) and Leukocyte activation specific antibodies (CD11a and CD35, Molecular Probes[®]). Inflammatory gene expression will be assessed via RT-PCR with a focus on evidence based gene targets including those identified as being most dramatically perturbed following severe injury from the *Glue Grant* study cohort including CD177, MMP8, lactotransferrin, haptoglobin, S100A8 (calgranulin), MYBL1

(myeloblastosis viral homologue, v-myb), KLRF1 (Killer cell lectin like receptor subfamily F, member 1), TGFBR3 (TGF- β receptor III subunit), and TCRA (T cell receptor α subunit).⁹⁴ These studies will be performed at a University of Pittsburgh FACS and RT-PCR core facilities which will be available 24 hours/day over the three years of the study.

J. Analysis Plan:

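### Plasmin is to be measured in serum, and section F implies serum for the related ELISA markers, so tranexamic acid left in the tube could lower the readings in the active arm only

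*Combined protocol and SAP*

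**What the plan says.** **Specimen.** For the Aim 3 markers, I.5.2 says that "serum plasmin levels, and plasmin mediated compliment activation (C3a and Factor B) and HMGB1 levels will be measured by ELISA plate assay". Plasmin is thus explicitly a serum measurement, with C3a and Factor B in the same sentence. For the Aim 2 markers, I.5.1 says that "D-dimer, activated Protein C levels and plasmin-antiplasmin complexes will be measured by ELISA plate assay" and names no specimen. Section F says: "Serum for cytokine and ELISA measurements will be batched and sent to the University of Pittsburgh on an annual basis". Section I.5, on everything except r-TEG and PT/INR, says that "all blood and serum samples will be spun, stored and batched at their respective institution", and that the material then goes to Pittsburgh for ELISA. No plasma tube, anticoagulant or time to centrifugation is given for any ELISA marker. Citrate appears only in the r-TEG background (C.4).

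**Mechanism.** C.7 says: "Tranexamic acid is a lysine analogue that interferes with binding of plasminogen to fibrin, which is required for plasmin activation". It also says that plasmin acts through complement activation.

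**Timing.** Sampling is within 6 hours of arrival and at 12 and 24 hours after injury with a 12-hour tolerance (I.5). A 72-hour draw is added for D-dimer, activated protein C and plasmin-antiplasmin. The active arm has already received a "1 gram bolus of tranexamic acid diluted in 100cc of normal saline" before arrival (H.3.1), and two of the three in-hospital regimens add an infusion lasting about 8 hours (H.3.2).

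**Hypotheses and analysis.** Secondary Hypotheses 1 and 3A predict improved or lower values of these markers on tranexamic acid. Hypotheses 4A and 4D predict the same for repeat dosing against the other regimens. J.2 and J.3 compare the groups directly.

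**The concern.** The drug under test inhibits the reaction being measured, and a serum tube gives that reaction a place to run after the blood has left the patient. If some plasmin forms on the clot before the sample is spun, placebo tubes can show it while tubes containing tranexamic acid show less. The group difference would then mix what happened in the patient with what happened in the tube.

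Three features make this more than a matter of assay noise. It would differ by arm, because only active-arm samples can contain the drug. It would point the way the hypotheses point. And randomisation and blinding do not protect against it, because the assigned treatment itself is the cause.

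Aim 3 is the most exposed, since it seeks inflammatory effects separate from the antifibrinolytic effect. An antifibrinolytic effect in the tube blurs exactly that separation. Once only serum has been banked, no later analysis can tell the two apart.

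**Working it through.** No figure in the plan depends on the specimen, so there is nothing to reproduce. The check sets the sections side by side and then illustrates sensitivity.

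**Step 1: which markers are in serum?**

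| Marker | Assay | Specimen named where measured | Specimen under F |
|---|---|---|---|
| Plasmin | ELISA (I.5.2) | Serum | Serum |
| C3a, Factor B | ELISA (I.5.2) | Same sentence as serum plasmin; not separately named | Serum |
| D-dimer, plasmin-antiplasmin | ELISA (I.5.1) | None; I.5 mentions both blood and serum | Serum |

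Serum is settled for plasmin. For the other four it follows from F, while I.5 leaves room for a different spun specimen.

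**Step 2: can the reaction run in the tube?** Serum is obtained by letting blood clot, which makes fibrin. C.4 itself notes that r-TEG must be run "within minutes of blood draw to prevent clot formation unless the addition of citrate occurs". By C.7, plasminogen needs fibrin to become plasmin and the drug interferes with that binding. The mechanism can therefore apply in a clotting tube. How much plasmin, D-dimer, plasmin-antiplasmin or complement fragment forms before the spin is not stated.

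**Step 3: can drug be present, and in which tubes?** The first draw follows the prehospital bolus in the active arm only. If the 12-hour tolerance applies to the 12-hour draw, its window is 12 − 12 = 0 to 12 + 12 = 24 hours after injury, so it can fall during or soon after the 8-hour infusion. Residual drug may then also differ between regimens. The documents give no clearance figure, so this is possible but not shown.

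**Step 4: how sensitive are the comparisons?** Inputs: 497 per arm (K.1), all assumed evaluable; two-sided 5% (J.2); no effect in the patient; an assumed in-tube shift of *d* standard deviations in one group. For *n* per group, Z has mean d√(n/2) and variance 1. The chance that the 95% interval excludes zero is

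P = Φ(d√(n/2) − 1.96) + Φ(−d√(n/2) − 1.96).

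With n = 497, √(n/2) = √248.5 = 15.76:

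- d = 0.05: mean 0.79, P = 0.124
- d = 0.1: mean 1.58, P = 0.351
- d = 0.2: mean 3.15, P = 0.884

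With fewer evaluable samples the figures fall. At an assumed 100 per arm they are 0.064, 0.109 and 0.293 for the same shifts.

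For two regimens of about 497/3 ≈ 166 each, √83 = 9.11. Shifts of 0.2 and 0.3 SD then give 0.445 and 0.780, if residual drug differs between regimens at all.

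**The case against.** **The specimen is less settled than it looks.** A reader might infer that all the ELISA markers are definitely measured in serum. The documents do not support that. I.5 lists blood alongside serum, I.5.1 names no specimen, and F is a logistics section. Tube detail may also sit in the Manual of Operations (mentioned in N.4) or in the training on sample processing (section O). This objection stands for every marker except plasmin. It does not rescue plasmin, where a manual calling for plasma would contradict I.5.2. For the others it leaves a conflict between F and I.5 that needs resolving anyway.

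**The artefact is inferred.** C.7 describes the drug's mechanism and C.4 a time limit on a bedside test. Neither reports plasmin generation in a serum tube. This stands: the documents support a possible bias and give no size.

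**A pure false positive is a strained scenario.** C.7 says the drug blocks plasmin activation, so inflation of a real effect is more plausible than creation of one from nothing. That is fair, and the percentages above do not measure inflation. But an in-tube shift would displace the estimate whatever the true effect.

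**The outcomes are minor and mostly reported as intervals.** J.2 prefers confidence limits to formal tests for secondary endpoints, I.5.2 is labelled exploratory, and hyperfibrinolysis is defined by r-TEG. This limits the consequence. It does not remove the bias, because a biased estimate carries its interval with it.

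**The affected list could be drawn differently.** Activated protein C should not be on it: C.7 links it neither to plasmin nor to fibrin binding. Conversely, C.7 does connect plasmin to cytokine release through complement. That route is more indirect, and the documents do not show that it operates in a tube.

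**Conclusion.** The concern holds as a possible bias that depends on arm and favours the hypotheses. It is firm as to specimen for plasmin, and conditional on section F for D-dimer, plasmin-antiplasmin, C3a and Factor B. It rests on three things: serum being clotted blood, the mechanism in C.7 operating in the tube before the spin, and drug still being present at the draw.

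Its size is unknown. At 497 evaluable per arm and with no effect in the patient, assumed shifts of 0.05, 0.1 and 0.2 SD give intervals excluding zero in about 12%, 35% and 88% of trials. These figures show that a small artefact would matter at this sample size. They are not an estimate of what will happen.

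Two stronger readings should be resisted. A reader might conclude that the mechanistic aims will come out falsely positive, but nothing in the documents establishes that the artefact is large enough. A reader might also take it as fact that the three regimens differ in residual drug at 12 hours, but there is no clearance information and the sampling window is wide. The bias should fade as drug clears, which may apply to the 72-hour draw. The primary outcome, 30 day mortality, is unaffected.

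**What to change.** - In I.5.2, replace serum with anticoagulated plasma as the specimen for plasmin.
- Reconcile F with I.5 and I.5.1 so that plasmin, plasmin-antiplasmin, D-dimer, C3a and Factor B are all measured in anticoagulated plasma, spun within a fixed, stated time of the draw. Take the anticoagulant for each marker from the assay kit's instructions; the documents give no basis for choosing one here.
- Serum may stay for the cytokine panel and HMGB1.
- Where only serum was banked, report those values of the five markers separately, flagged as possibly affected by inhibition in the tube, and do not use them as evidence for Secondary Hypotheses 1, 3A, 4A or 4D. They need not be discarded.

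The cost is a different tube at the same draw and a change of wording. The change has to come before samples are taken, because banked serum cannot be turned back into plasma.

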development of multiple organ failure.⁸³ (**Figure 10.**) More recent work demonstrates the utility of air medical tissue oximetry and the ability it has to predict operative intervention or blood transfusion in the first 24 hours following injury.⁸⁴ (**Figure 11.**) A recent study which was presented at the 2012 AAST annual meeting utilizing Gluegrant dataset demonstrated that overly aggressive prehospital crystalloid use was associated with an independent greater risk of early coagulopathy and mortality in patients who were normotensive (SBP>90mmHg) while a trend towards benefit and lower risks of poor outcome were found in patients with prehospital hypotension (SBP<90mmHg). (Journal of Trauma and Acute Care Surgery. *In Press*, 2013, **Figure 12.**)

D.4. Feasibility of the trial: The collaborative environment between the Departments of Surgery and Emergency Medicine at the University of Pittsburgh unifies prehospital clinical research expertise with hospital based acute care research expertise and will provide the main impetus for the successful execution of the current proposal. The principal investigators participation and involvement in the Inflammation and the Host Response to Injury Program, (Glue grant), the Resuscitation Outcomes Consortium (ROC) and recent funding (proposal #11152002, W81XWH-12-2-0023) from the Department of Army for the ‘Prehospital Use of Plasma for Traumatic Hemorrhage (PUPTH) Program’ documents and verifies the robust nature of the University of Pittsburgh’s multi-center research collaborations and expertise in prehospital investigations, the clinical research infrastructure that is available and the institutional and departmental support to promote and allow the successful execution and completion of the proposed aims that will provide important knowledge into the mechanisms and appropriate dosing of tranexamic acid that maximize its beneficial effects.

D.5. Feasibility of air medical service intervention at the University of Pittsburgh: Under the direction of [name], Co-Principal Investigator of this proposal, the air medical service at the University of Pittsburgh is the busiest non-profit flight service in the country and has a significant track record of prospective trials and interventions in the prehospital arena.^{76,78,79,82-86} The air medical service at the University of Pittsburgh has 14 air medical bases which have flown over 1,600 injured patients to Presbyterian Hospital, the busiest level 1 trauma center in the state of Pennsylvania, over the last 12 months (2012 data). The DOD funded PAMPer trial (Prehospital Air Medical Plasma trial) under the auspices of the PUPTH Program will utilize only 4 out of the 14 air medical bases which reside closest to blood banking affiliates due to the requirement of thawed plasma for the multi-center trial. The remaining 10 helicopter bases will be utilized for the current proposal providing one of largest patient populations available across the country for an air medical prehospital intervention. It is this extensive prehospital investigation expertise and experience that will promote and allow the successful completion of the aims of the proposal.

D.6. Clinical research infrastructure and coordinating center expertise of the University of Pittsburgh: The Department of Surgery at the University of Pittsburgh has interdepartmental research affiliations with the Department of Critical Care Medicine and the Department of Emergency Medicine and has spearheaded the Multidisciplinary Acute Care Clinical Research Organization (MACRO). MACRO is a unique, interdepartmental resource with laboratory facilities, an experienced and professionally-trained staff of 11 clinical research coordinators, 15 research associates and 24 hour around the clock screening capabilities. They have extensive experience with data entry, multi-center data coordination, training, IRB liaison needs, web-based data entry platform creation and specimen management and storage. MACRO follows a cost center model and provides ‘cost-neutral’ services to clinical investigators from diverse specialties in order to conduct clinical and translational research. Currently, Over 71 principal investigators and co-investigators from 9 different departments currently utilize MACRO services. Thru 2012 alone, MACRO’s services were utilized for 14

[figure not shown]

Fig 11. ROC curve revealing ability of prehospital tissue oximetry to predict operative intervention or blood transfusion in first 24 hours post-injury

[figure not shown]

Fig 12. Forest plot depicting independent mortality risks associated with high volume prehospital crystalloid in hypotensive and non-hypotensive

interventional trials and 11 observational trials. MACRO has been the clinical research infrastructure utilized for the institutions involvement in the *Gluegrant* and *ROC* studies and is the infrastructure that is being utilized for the multi-center coordination of the DOD funded PAMPPer trial. It is with the dedicated clinical research infrastructure provided by MACRO at the University of Pittsburgh that the aims of the current proposal can successfully be completed.

D.7. Feasibility of patient recruitment for the trial: As demonstrated by being essential participants of both the *Gluegrant* and *ROC* studies, the departments of Surgery and Emergency Medicine at the University of Pittsburgh have a significant track record of successful patient recruitment and enrollment in large prehospital and in hospital prospective trials for traumatic injury. Regarding the specifics of the current proposal, over the last 12 months, the air medical services that will be utilized for this trial has transported > **150 patients** meeting the specific inclusion and exclusion criteria for this proposal (SBP < 90mmHg and tachycardia - > 110 bpm). Participating centers have been chosen with similarly busy air medical services and with a history of involvement with the *Gluegrant*, *ROC* or with other multi-institutional clinical research experience. *It is under the auspices of the collaborative clinical research environment of the University of Pittsburgh and these busy participating trauma centers that the specific objectives and aims of the current proposal can successfully be accomplished.*

E. Objectives/Hypotheses

E.1. Study Rationale: Traumatic injured patients continue to be plagued with uncontrolled hemorrhage resulting in significant morbidity and early mortality. A primary driving force for this unbridled hemorrhage is known to be the early coagulopathy which complicates severe injury. Trauma induced coagulopathy has been postulated to be an equilibrium imbalance between pro and anticoagulant factors, platelets, endothelium and fibrinolysis soon after injury. Recent evidence demonstrates that the early use of the antifibrinolytic agent tranexamic acid after trauma center arrival results in improved survival in patients at risk for bleeding. Bringing this proven treatment to the prehospital arena and intervening earlier in those patients who would otherwise not be candidates for treatment has the real potential to further reduce or prevent the vicious hemorrhagic cascade, improve clinical outcomes and provide insight into the underlying mechanisms responsible for and which maximize its benefit.

E.2. Primary Objective: To determine the effect of prehospital tranexamic acid infusion (1 gram over approximately 10 minutes) as compared to placebo during emergency medical transport in patients at risk of traumatic hemorrhage on 30 day mortality.

E.2.1. Primary Aim#1: Determine whether prehospital tranexamic acid as compared to placebo reduces 30 day mortality in patients at risk for traumatic hemorrhage.

Primary Hypothesis 1: Prehospital tranexamic acid as compared to placebo will reduce 30 day mortality in patients at risk of traumatic hemorrhage

E.3. Secondary Objectives: To determine the effect of prehospital tranexamic acid infusion (1 gram over approximately 10 minutes) as compared to placebo during emergency medical transport in patients at risk of traumatic hemorrhage on the incidence of hyperfibrinolysis (estimated percent lysis > 7.5%, first 30 minutes by rapid-thromboelastography) acute traumatic coagulopathy (ATC), early markers of coagulopathy, the incidence of 24 hour mortality, acute lung injury, multiple organ failure and development of nosocomial infection, shock parameters and resuscitation/transfusion requirements, platelet and leukocyte activation and the early inflammatory response and to determine whether different dosing regimens of tranexamic acid upon arrival in the hospital are associated with improvements in hyperfibrinolysis, coagulopathy, clinical outcomes and the early inflammatory response.

E3.1. Secondary Aim#1: Determine whether prehospital tranexamic acid as compared to placebo reduces the incidence of hyperfibrinolysis (estimated percent lysis > 7.5%), acute traumatic coagulopathy (ATC, presenting INR > 1.4), improves PT measurements and additional r-TEG parameters, D-dimer levels, activated Protein C levels, and plasmin-antiplasmin complexes.

Secondary Hypothesis 1: Prehospital tranexamic acid as compared to placebo will reduce the incidence hyperfibrinolysis (estimated percent lysis > 7.5%), reduce the incidence of patients with an arrival INR > 1.4, improve PT and additional presenting r-TEG parameters of coagulopathy including ACT, r-value, k-time, α -angle, maximal amplitude (MA) and G-values and D-dimer levels, activated Protein C levels and plasmin-antiplasmin complexes.

E.3.2. Secondary Aim#2: Determine whether prehospital tranexamic acid as compared to placebo results in a lower incidence of 24 hour mortality, acute lung injury, multiple organ failure, nosocomial infection, early seizures, pulmonary embolism, shock parameters and early resuscitation and transfusion requirements.

Secondary Hypothesis 2A: Prehospital tranexamic acid as compared to placebo will reduce the incidence of 24 hour and 30 day mortality, acute lung injury, multiple organ failure, nosocomial infection, early (24hr) seizures and in-hospital pulmonary embolism.

Secondary Hypothesis 2B: Prehospital tranexamic acid as compared to placebo will improve presenting base deficit, 24 hour crystalloid requirements and reduce 6 hour and 24 hour blood and blood component transfusion requirements (PRBC, FFP and platelets).

E.3.3. Secondary Aim #3: To investigate potential novel mechanisms by which tranexamic acid alters the inflammatory response to injury independent of effects on hyperfibrinolysis. Investigations of the effects of tranexamic acid on inflammation will include analysis of platelet and leukocyte activation via flow cytometry, measurements of plasmin levels and subsequent plasmin mediated complement activation and the early inflammatory cytokine response to trauma.

Secondary Hypothesis 3A: Prehospital tranexamic acid as compared to placebo will reduce plasmin levels and markers of platelet and leukocyte activation measured by flow cytometry (FACS) and result in a plasmin mediated reduction of complement activation as measured by C3a and Factor B levels.

Secondary Hypothesis 3B: Prehospital tranexamic acid as compared to placebo will attenuate trauma-induced pro-inflammatory changes and immunosuppression by reducing the early inflammatory cytokine response (GM-CSF, IFN- γ , IL-1 β , IL-2, IL-4, IL-5, IL-6, IL-8, IL-10 and TNF- α), HMGB1 levels and early inflammatory gene responses as measured by RT-PCR.

E.3.4. Secondary Aim#4: Determine whether different dosing regimens of tranexamic acid upon arrival in the hospital are associated with improvements in hyperfibrinolysis, markers of coagulopathy, clinical outcomes, platelet and leukocyte activation and the early inflammatory response.

Secondary Hypothesis 4A: Repeat dosing of 1 gram of tranexamic acid followed by 1 gram over approximately 8 hours after hospital arrival in patients who have already received 1 gram of prehospital tranexamic acid will lower the incidence of 12 hour (from arrival) hyperfibrinolysis (estimated percent lysis > 7.5%), coagulopathy (INR > 1.4) and improve r-TEG markers of coagulopathy, D-dimer levels, activated protein C levels and plasmin-antiplasmin complex levels as compared to standard dosing of tranexamic acid (1 gram over approximately 8 hours) or abbreviated dosing (no additional tranexamic acid).

Secondary Hypothesis 4B: Repeat dosing of 1 gram of tranexamic acid followed by 1 gram over approximately 8 hours after hospital arrival in patients who already received prehospital tranexamic acid will lower the incidence of 24 hour and 30 day mortality, acute lung injury, multiple organ failure and nosocomial infection as compared to standard dosing or abbreviated dosing.

Secondary Hypothesis 4C: Repeat dosing of 1 gram of tranexamic acid followed by 1 gram over approximately 8 hours after hospital arrival in patients who already received prehospital tranexamic acid will reduce 12 hour (from arrival) base deficit, 24 hour crystalloid requirements and 6 hour and 24 hour blood and blood component transfusion requirements (PRBC, FFP and platelets) as compared to standard dosing or abbreviated dosing.

Secondary Hypothesis 4D: Repeat dosing of 1 gram of tranexamic acid followed by 1 gram over approximately 8 hours after hospital arrival in patients who already received prehospital tranexamic acid will reduce 12 hour and 24 hour (from arrival) markers for platelet and leukocyte activation, plasmin

levels, markers of complement activation, HMGB1 levels and the early inflammatory cytokine response as compared to standard dosing or abbreviated dosing.

F. Project Milestones:

The proposal is for a 3 year trial. The FDA approval process will be initiated after notification of proposal funding. Community notification and other procedures associated with exception from consent for emergency research will be initiated and completed prior to IRB approval at all institutions. Following final IRB approval a 1.5 month startup period will be utilized to verify and educate all centers prior to beginning enrollment. A data entry web based platform will be created during this same time period. Enrollment will occur for 33 months (2.75 years) with prospective data entry of laboratory and TEG measurements, clinical outcomes, transfusion requirements and demographic and injury characteristics. Serum for cytokine and ELISA measurements will be batched and sent to the University of Pittsburgh on an annual basis. We expect approximately 70 patients per year per institution on average. Flow cytometry for platelet and leukocyte activation and RT-PCR may be performed at the University of Pittsburgh prospectively on a subset of patient samples. Enrollment will be monitored on a semi-annual basis for each participating center. Data safety and monitoring over the course of the clinical trial will fall under the responsibility of an independent data safety and monitoring board (DSMB). Interim analysis will occur at 33% and 66% of patient enrollment. A 1.5 month data cleaning and wind down will occur once enrollment has been completed, allowing data analysis and manuscript preparation.

G. Military Significance/Public Purpose:

Despite the significant advances in trauma care delivery and post-injury management practices which have occurred over the last decade, uncontrolled hemorrhage remains one of the leading causes of trauma related deaths.^{4,5,87,88} Recent evidence demonstrates that the early use of the antifibrinolytic agent tranexamic acid after trauma center arrival results in improved survival in patients at risk for bleeding.⁴¹ Bringing this proven treatment to the prehospital arena and intervening earlier in those patients who would otherwise not be candidates for treatment has the real potential to further reduce or prevent the vicious hemorrhagic cascade, improve clinical outcomes and provide insight into the underlying mechanisms responsible for and which maximize its benefit. This potential knowledge base would be dramatically beneficial to both military and civilian trauma systems. It is in both these settings where the prehospital phase of treatment represents a relatively novel arena for new interventions. The results provided by the successful completion of this proposal will have paramount implications for both military and civilian injured patients as control of hemorrhage and delay to definitive care represent major impediments for both populations. This proposal will provide needed insight into the consequences of early tranexamic acid intervention in these significantly injured patients when these impediments exist.

H. Research Design and Methods

H.1. Study Design/Setting: The study will be a 3 year, multi-center, blinded, randomized trial utilizing level-1 trauma centers with busy emergency medical transport services with a clinical research track record. For patients at risk of hemorrhage being transported by emergency medical transport, the infusion of 1 gram of tranexamic acid over approximately 10 minutes in the prehospital setting will be compared to placebo. The University of Pittsburgh Medical Center (UPMC) will be both the clinical outcome and data coordinating center. Each individual institution will perform point of care rapid TEG analysis and coagulation measurements on site. UPMC presbyterian is the busiest level-1 trauma center in the state of Pennsylvania and is affiliated with the largest non-profit air medical service in the country with an extensive track record of multi-center, in-

